7. DATA MANAGEMENT

7.1 Data Collection and Processing

Subject data will be collected in a secure electronic data capture (EDC) system via the Internet. All pertinent data will be entered by the study site personnel into the electronic Case Report Forms (eCRFs). A unique subject ID number will be assigned to each subject. Every reasonable effort should be made to complete data entry within five days of data collection. Any data discrepancies may be queried during ongoing review of data by RefleXion Medical personnel or its designees, or may be identified and queried during routine monitoring visits. Data monitoring will be performed to verify data accuracy and ensure queries are resolved. The Principal Investigator or Sub-investigator must ensure the accuracy and completeness of the recorded data and then provide his/her electronic signature on the appropriate CRFs. Changes to data previously submitted to the sponsor will require a new electronic signature by the investigator to acknowledge/approve the changes.

Results from independent reviewers will also be entered into the EDC system and will be electronically signed by the reviewer responsible for entering this data. Ongoing data review will be performed to

identify possible data discrepancies. Manual and/or automatic queries will be created in the EDC system and will be issued to responsible parties for appropriate resolution.

8. MONITORING PROCEDURES

8.1 Monitoring

Monitoring visits to the clinical sites will be made periodically during the study, to ensure that all aspects of the current, approved protocol/amendment(s) are followed. Original source documents will be reviewed for verification of data in the electronic database. The Investigator/institution guarantees direct access to original source documents by RefleXion Medical personnel, its designees, and appropriate regulatory authorities. In the event that the original medical records cannot be obtained for a subject that is seen by a non-study physician at a non-study institution, photocopies of the original source documents must be made available for review.

It is important that the Investigator and/or relevant study site personnel are available during the monitoring visits and that sufficient time is devoted to the process. In order to perform her or his role well, the monitor must be given access to primary subject medical records, which support the data that has been entered into the study CRFs. Access to Protected Health Information (PHI) by the study monitor will be disclosed to the subject within the Informed Consent Form.

8.2 Auditing

The study may be subject to a quality assurance audit by RefleXion Medical or its designees, as well as inspection by appropriate regulatory authorities. It is important that the Investigator and relevant study personnel are available during any audits and that sufficient time is devoted to the process.

8.3 Device Accountability

Device accountability records must be maintained at the study site. Investigational features of the RMRS system (BgRT mode) will be available after all essential documents are collected, the Site Initiation Visit and training of all required study personnel is completed, and the site is approved to enroll. In some circumstances, at the discretion of the Clinical Project Manager, the investigational device availability may precede the Site Initiation Visit, if a site is anticipated to complete all requirements to be eligible to begin enrollment during the visit.

Study personnel authorized to operate BgRT mode will be identified on the Delegation of Authority Log. The operator will be instructed and trained to utilize BgRT mode only for study subjects. Operator training and understanding of study requirements will be documented in the electronic Trial Master File (eTMF) per Study Master File Index (SMFI). The system software will ensure via login credentials that BgRT mode is only accessible to delegated study personnel. Additionally, the BgRT mode will display an investigational

device notification indicating that the use is limited by Federal law to investigational use. The operator will need to acknowledge the notification to be able to move forward with the BgRT mode.

9. ADVERSE EVENTS

9.1 Adverse Event Definitions and Classification

Term	Definition	Reference
Adverse Event (AE)	Any untoward medical occurrence, unintended disease or injury, or untoward clinical signs (including abnormal laboratory findings) in subjects, users or other persons, whether or not related to the investigational medical device.	ISO 14155
	NOTE 1 This definition includes events related to the investigational medical device or the comparator.	
	NOTE 2 This definition includes events related to the procedures involved.	
	NOTE 3 For users or other persons, this definition is restricted to events related to investigational medical devices.	
Adverse Device Effect (ADE)	Adverse event related to the use of an investigational medical device. NOTE 1 This definition includes adverse events resulting from insufficient or inadequate instructions for use, deployment, implantation, installation, or operation, or any malfunction of the investigational medical device. NOTE 2 This definition includes any event resulting from use error or from intentional misuse of the investigational device.	ISO 14155
Serious Adverse Event (SAE)	 Adverse event that 1. led to death, 2. led to serious deterioration in the health of the subject, that either resulted in a. a life-threatening illness or injury, or b. a permanent impairment of a body structure or a body function, or 	ISO 14155

Term	Definition	Reference
	c. in-patient or prolonged hospitalization, or	
	 medical or surgical intervention to prevent life- threatening illness or injury or permanent impairment to a body structure or a body function, 	
	 led to fetal distress, fetal death or a congenital abnormality or birth defect. 	
	4. NOTE Planned hospitalization for a pre-existing condition, or a procedure required by the clinical investigational plan, without serious deterioration in health, is not considered a serious adverse event.	
Serious Adverse Device Effect (SADE)	Adverse device effect that has resulted in any of the consequences characteristic of a serious adverse event.	ISO 14155
Unanticipated Adverse Device Effect (UADE)	Any serious adverse effect on health or safety or any life- threatening problem or death caused by, or associated with a device, if that effect, problem, or death was not previously identified in nature, severity, or degree of incidence in the investigational plan or application (including a supplementary plan or application), or any other unanticipated serious problem associated with a device that relates to the rights, safety, or welfare of subjects.	21 CFR Part 812

Underlying diseases are not reported as Adverse Events (AEs) unless there is an increase in severity or frequency during the course of the study. Death is not an adverse event but should be reflected as an outcome to another specific AE. Any AE experienced by the study subject after enrollment whether during or subsequent to the study procedures must be collected and recorded in the (e)CRF.

9.1.1 Relationship of Adverse Event to the Study Device and/or Procedures

The investigator must assess the relationship of the adverse event to the study device using the following criteria:

Unrelated: the adverse event is determined to be due to a concurrent illness or effect of another device/drug and is not related to the investigational device.

Possible: the adverse event is determined to be potentially related to the investigational product, and an alternative etiology is equally or less likely compared to the potential relationship to investigational product.

Probable: there is a strong relationship to investigational product, or recurs on re-challenge, and another etiology is unlikely

Highly probable: there is no other reasonable medical explanation for the event.

The investigator must assess the relationship of the adverse event to the study procedures using the following criteria:

Unrelated: the adverse event is determined to be due to a concurrent illness or effect of another device/drug and is not related to the study procedure.

Possible: the adverse event is determined to be potentially related to the investigational product, and an alternative etiology is equally or less likely compared to the potential relationship to the study procedure.

Probable: there is a strong relationship to study procedure, or recurs on re-challenge, and another etiology is unlikely

Highly probable: there is no other reasonable medical explanation for the event.

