5. STUDY POPULATION

- 5.1 Selection Criteria
- 5.1.1 Inclusion Criteria
- 1. Age greater than 21 years
- 2. A new or prior diagnosis of biopsy-proven cancer with a solid tumor (non-hematologic, non-lymphoma)
- 3. At least one active tumor in the bone or lung which is either the primary tumor or metastatic lesion determined either by biopsy or imaging suspicious of active disease
- 4. Target tumor size ≥2cm and ≤5cm

- Target lesion in the bone or lung that is discrete and assessed by investigator to be FDG-avid (i.e. SUV_{max}≥6 on third-party diagnostic PET/CT performed within 60 days with no new intervening oncologic therapies)
- 6. ECOG Performance Status 0-3
- 7. Must have completed any other oncologic therapies at least 15 days prior to planned start of study procedures (preferably 30 days) and must have no plans to initiate systemic therapy until after study follow up is complete -OR- must be recorded by physician to have an active candidate lesion that is unresponsive to ongoing systemic therapy
- 8. Females of childbearing potential should have negative urine or serum pregnancy test within 14 days prior to initiation of study scans.
- 9. Demonstrate adequate organ function:
 - a. Absolute neutrophil count (ANC) > 1,500 /mcL
 - b. Platelets > 50,000 / mcL
 - c. Hemoglobin > 8 g/dL
 - d. No gross hematuria
- 10. For Cohort II only: Patient is dispositioned to undergo SBRT to a bone or lung tumor

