This argument for tolerability, which is based upon first principles of radiation safety, is further supported by empiric evidence from human and animal studies. Cox et al. conducted a phase I trial of very high doses of FDG to determine whether the radiation emitted by FDG could be utilized for therapeutic effect²⁰. In their study, three patients were given progressively higher doses of FDG (100 mCi/m², 150 mCi/m², and 200 mCi/m²) with a single injection. With a median follow-up of 6 months, no dose limiting toxicities were observed. Notably, the third patient in the study received 400 mCi of FDG. Multiple investigations have utilized serial weekly FDG PET scans over a 6 week course of fractionated radiotherapy to assess early tumor response during treatment; although toxicity was not a formal endpoint in these imaging studies, nonetheless no unexpected adverse events attributable to multiple administrations of the tracer were reported^{21,22}. Moadel et al. determined that the dose-limiting organ in human patients treated with high-dose FDG would be the red marrow using the Medical Internal Radionuclide Dosimetry Formalism, and further determined that the tolerance dose that would result in 5% risk of red marrow suppression at 5 years (TD 5/5) was 4760 mCi^{23,24}. In addition to these human investigations, a number of animal studies of very high FDG doses (up to 6 mCi per 20 g mouse) have, to date, not resulted in any observable toxicity²².

Although this evidence and first principles of radiotherapy safety provide reassurance that multiple FDG administrations at a diagnostic dose are unlikely to cause measurable toxicity, nonetheless this investigation seeks to provide additional evidence for the safety of multiple FDG administrations. Cohort II will seek to capture evidence regarding the tolerability of multiple FDG administrations through standard grading of toxicities during therapy. Study subjects will be observed for potential FDG administration related toxicity and AEs related to the organs at theoretical risk, which include the bladder and bone marrow. These adverse events may include anemia, thrombocytopenia, bleeding, lymphopenia, neutropenia, hematuria, bladder spasms, transient hypotension, hypo- or hyperglycemia and/or had transient increases in alkaline phosphatase.

Other potential FDG exposure related risks and mitigations include:

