13.2.4 Safety Analyses

Extent of FDG exposure will be summarized by number of doses, cumulative dose, any dose interruption and dose reduction. Safety will be assessed through AEs, changes in laboratory parameters, and vital signs. AEs will be coded using the Medical Dictionary for Regulatory Activities (MedDRA); AE severities will be graded using the CTCAE criteria.

All AE data will be listed. Notably, actual delivery of BgRT treatment to the patient is not part of this investigation. All treatment-emergent AEs (TEAEs), defined as adverse events not present prior to FDG exposure and study procedures, will be summarized, as follows:

- All TEAEs by worst Grade
- All TEAEs related to the study device and/or FDG exposure by worst Grade
- All Grade 3/4/5 TEAEs
- All Treatment Emergent SAEs by worst Grade
- All Related Treatment Emergent SAEs related to study device and/or FDG exposure by worst Grade

Observed and changes from baseline in laboratory values will be summarized. Laboratory values outside the corresponding normal ranges will be flagged in listings.

Observed and Changes from baseline vital signs and ECOG data will be summarized similarly as laboratory values.

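### The causality scales in section 9.1.1 have no level for an event that may be related but has a more likely alternative cause

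*Combined protocol and SAP*

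**What the plan says.** Section 9.1.1 makes the rating mandatory: "The investigator must assess the relationship of the adverse event to the study device using the following criteria". A second scale with the same four levels follows for the study procedures. The levels are:

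- *Unrelated* (device): "the adverse event is determined to be due to a concurrent illness or effect of another device/drug and is not related to the investigational device". The procedure version is parallel.
- *Possible* (device): the event is potentially related, and "an alternative etiology is equally or less likely compared to the potential relationship to investigational product". On the procedure scale the restriction is "an alternative etiology is equally or less likely compared to the potential relationship to the study procedure".
- *Probable* (device): "there is a strong relationship to investigational product, or recurs on re-challenge, and another etiology is unlikely". The procedure version is parallel.
- *Highly probable* (both scales): nothing else reasonably explains the event.

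Neither scale has an unlikely, remote or not-assessable level, and no section gives a default for an event that meets no definition.

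Section 13.2.4 plans five summaries of treatment-emergent adverse events (TEAEs). Two are restricted by relationship: "All TEAEs related to the study device and/or FDG exposure by worst Grade", and its counterpart for serious events. The section does not say which levels count as related. Section 9.1 defines an adverse device effect (ADE), and through it a serious adverse device effect (SADE), by relatedness to use of the device.

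**The concern.** A causality scale should give every event exactly one level. If one kind of event has none, investigators must improvise, and the related-event tables then depend partly on who did the rating.

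Competing causes are plausible in this trial. Cohort II subjects receive SBRT, with FDG given within 96 hours before the first and final fractions (sections 6.3.5 and 6.3.6). Inclusion criterion 7 also admits a subject with an "active candidate lesion that is unresponsive to ongoing systemic therapy", and section 6.3.1 leaves continuation of that therapy to the treating physician. Section 10.2 says of the toxicities to be watched: "These adverse events may include anemia, thrombocytopenia, bleeding, lymphopenia, neutropenia, hematuria". Sections 4.3 and 10.2 also describe the expected risk from FDG as very small. An investigator who accepts this may well think another cause of a cytopenia likelier and still be unable to exclude FDG.

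The study has a single arm, so no comparator rate helps to separate FDG or device effects from background. Among the planned summaries, only the two related-event tables attempt that separation, and they rest on this scale.

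**Working it through.** No figure in the plan is at issue and no calculation applies. The check is logical and has two steps.

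**Step 1. Test one event against each level.** Take an event that is potentially related, where the investigator thinks an alternative cause more likely but cannot exclude the device or procedure.

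| Level | What it requires | Met? |
|---|---|---|
| *Unrelated* | Another cause determined, and no relationship | No: a relationship has not been excluded |
| *Possible* | Alternative no more likely than the device or procedure | No: the alternative is more likely |
| *Probable* | Strong relationship or recurrence on re-exposure, and alternative unlikely | No: the alternative is not unlikely |
| *Highly probable* | No other reasonable explanation | No: there is one |

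The event fits 0 of 4 levels. The result is the same on both scales, because *Possible* carries the same restriction on each.

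**Step 2. Trace where the rating is used.**

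| Output | Filtered on relationship? |
|---|---|
| All TEAEs by worst grade (13.2.4) | No |
| Related TEAEs by worst grade (13.2.4) | Yes |
| Grade 3 to 5 TEAEs (13.2.4) | No |
| Treatment-emergent serious events (13.2.4) | No |
| Related treatment-emergent serious events (13.2.4) | Yes |
| Listing of all adverse events; laboratory changes from baseline (13.2.4) | No |
| Cohort II bladder and bone marrow endpoint (3.2.2, item 4) | No |
| ADE and SADE status (9.1) | Yes, for the device |

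If the event is coded *Unrelated*, it drops out of 2 of the 5 TEAE summaries and stays in the others it qualifies for and in the listing. If it is coded *Possible* despite the wording, and *Possible* counts as related, it stays in every summary it qualifies for. The same clinical judgement can therefore produce different related-event tables.

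The trace also shows a mismatch. The filtered tables concern the device and FDG exposure, while section 9.1.1 provides scales for the device and the procedures. Section 9.2 groups procedure and FDG effects together, which suggests that the procedure scale is meant to serve for FDG, but no section says so.

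**The case against.** The strongest reply is that the scale can be read as a deliberate cut at equal likelihood. On that reading, an investigator who finds another cause more likely has in effect determined the event to be due to it, and *Unrelated* is the intended level. This is a possible working practice. But *Unrelated* also requires that the event is not related, and preferring one cause does not exclude the other. The reading supports the expectation that ratings will lean towards *Unrelated*; it does not make the scale exhaustive.

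A second reply is that little depends on the rating. Much of this stands. The related-event tables are descriptive, with no test or stopping threshold attached. Serious events go to the sponsor within 24 hours whatever their relationship (section 9.3), and the Safety Monitoring Committee reviews adverse and serious adverse events in both cohorts (section 11.1). Unfiltered outputs do not, however, repair the filtered ones.

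Four stronger readings are tempting and should not be drawn:

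- A reader might infer that such events are forced into *Unrelated*. The wording of *Unrelated* excludes them too, so that outcome is likely rather than dictated.
- A reader might infer that this will be the usual case. The documents give no adverse event rates. The SBRT toxicities named in section 9.2 do not include cytopenias or urinalysis abnormalities, which appear under procedure and FDG effects. Ongoing systemic therapy is only one branch of inclusion criterion 7.
- A reader might infer that bladder and bone marrow monitoring is biased low. That endpoint uses blood counts, urinalysis and directed CTCAE grading at baseline and follow-up, with no relationship filter.
- A reader might take 1/22 = 4.5% to 1/8 = 12.5% as the size of the problem. That range is only the weight of any one subject in a Cohort II of 8 to 22, and says nothing about how many events fall in the gap.

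**Conclusion.** The point holds as a defect in a stated rule: both scales leave a potentially related event with a likelier alternative cause without a level. The consequence is inconsistent rating, probably tilted to *Unrelated* because *Possible* expressly bars a likelier alternative. That can understate the two related-event summaries and affect ADE and SADE classification. The primary endpoints are untouched.

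The size cannot be stated, because the documents do not allow the number of affected events to be estimated. The direction rests on three assumptions: investigators apply the *Possible* wording literally, *Possible* and above are tabulated as related, and the device rating in section 9.1.1 decides ADE status.

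**What to change.** In section 9.1.1, on both scales, reword *Possible* to cover any event for which a relationship cannot be ruled out, including when another cause is considered more likely. *Unrelated* is then kept for events where a relationship is excluded. On the procedure scale, the new wording should refer to the procedure throughout; the present first clause of *Possible* there names the investigational product.

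In section 13.2.4, state that related means *Possible*, *Probable* or *Highly probable*, and state which section 9.1.1 scale supplies relatedness to FDG exposure. These two statements can also go in the SAP, which section 13.3 says is finalized before database lock.

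The cost is protocol and eCRF pick-list wording. If events have already been rated under the present definitions, those coded *Unrelated* would need a second look so that one rule applies throughout. The downside is that related-event counts may rise, by an amount that cannot be predicted, and *Possible* becomes less discriminating because it will hold both even-odds and less likely relationships.

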9.2 Potential Adverse Events

Study subjects will continue to receive standard of care treatments throughout the study, which are not part of study procedures. The treating physician will counsel the subjects on the risk of the treatments including the risk of surgery, radiation therapy and any other treatment appropriate for their type and stage of cancer. Toxicities commonly associated with such treatments include but are not limited to fatigue, nausea, vomiting, anorexia, and weight loss. Some of these symptoms can also be due to tumor progression.

Adverse events related to SBRT radiotherapy for the treatment of metastases are dependent on the location of the metastases treated, as well as from exposure of surrounding normal tissues. Fatigue and skin problems such as dryness, itching, blistering or peeling is likely to occur for all treated metastases and should be transient, lasting < 8 weeks. Patients who are receiving standard of care radiotherapy for lung tumors may experience difficulty swallowing, shortness of breath, breast or nipple soreness, shoulder stiffness and/or radiation pneumonitis characterized by cough, fever, and fullness of the chest associated with radiographic infiltrate. Anticipated adverse events for bone tumor patients who are undergoing standard of care radiotherapy may include erythema, desquamation, alopecia, fracture, and inflammation in nearby organs-at-risk (i.e. esophagitis, enteritis, pneumonitis, etc.).

Study procedure and/or FDG exposure related AE may include:

- 1. Allergic reaction, including itching, edema and rash, as well as brief or transient hypotension
- 2. Hypoglycemia and hyperglycemia, especially in patients with Diabetes Mellitus
- 3. Laboratory abnormalities, including increase in alkaline phosphatase, urinanalysis abnormalities, and cytopenias

Appropriate clinical assessments will be performed as indicated to identify all AEs. AEs will be graded according to the NCI Common Terminology Criteria for Adverse Events (CTCAE) version 5. Signs and symptoms of existing disease progression will not be considered AEs. Development of new cancer after the inclusion of subject in the study will be considered an AE.

Event Classification	Communication Method to RefleXion Medical	Communication Timeline to RefleXion Medical
UADE*	Complete AE (e)CRF page including UADE question with all available new and updated information.	Within 24 hours of first becoming aware of the event.
SAE*	Complete AE (e)CRF page including UADE question with all available new and updated information.	Within 24 hours of first becoming aware of the event.
AE	Complete AE (e)CRF page	As soon as possible.
Device Failure and Malfunction	Complete applicable CRF fields/pages with all available new and updated information	Within 24 hours of first becoming aware of the event.

